6.3.3.8 Change in patient resource use (eg, work/school attendance, visits to doctor/hospital)

Change in patient resource use (eg, work/school attendance, visits to doctor/hospital) from baseline will be summarized descriptively.

6.4 Pharmacodynamic Analysis

6.4.1 Antithrombin

AT levels and AT lowering (% lowering from baseline) will be summarized descriptively. In addition, mixed model repeated measures (MMRM) analyses will be performed on AT lowering with fixed effects of treatment arm, randomization strata of number of bleeding episodes in the 6 months prior to study entry (≤ 10 vs > 10), visit and baseline AT level. A suitable covariance structure will be chosen to minimize Bayesian information criteria (BIC).

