#### 1.4. Dose Rationale

Dose selection was guided by the principle of identifying an optimal dose that is both well-tolerated and efficacious. The fitusiran dose proposed for Phase 3 development was identified based on observed data from ongoing clinical studies, as well as extensive clinical simulations and modeling. The key PD and clinical parameters used to support the dose selection include decreases in AT activity, the most proximate and direct PD effect of fitusiran, as well as increases in thrombin generation and decreases in ABR.

Observed data from Phase 1 and Phase 1/2 studies in patients with hemophilia A and B, with or without inhibitors, and PK/PD modeled data, support selection of a fixed dose of 80 mg for this study, as subcutaneously administered once-monthly.

In observed data from Phase 1 and Phase 1/2 studies, monthly equivalent doses or monthly doses ranging from 0.045 mg/kg to 1.8 mg/kg and fixed doses of 50 mg and 80 mg have been evaluated. A clear dose response trend of increased AT lowering is evident, with approximately 10% to 20% residual AT activity at a dose of 1.8 mg/kg and at fixed doses of 50 mg and 80 mg subcutaneously administered once monthly. These data suggest that the maximum AT lowering achieved as a function of the dose administered reaches an asymptote at  $\sim 90\%$  AT lowering and that it is unlikely higher doses will achieve meaningfully greater AT lowering. In addition, both the 50 mg and 80 mg fixed doses produced substantial increases in peak thrombin generation, which approach the lower end of the normal range, but do not exceed the normal range.

Dose-response modeling analyses are supportive of the observed data. A repeated time to event model was used to evaluate the relationship between AT lowering and the anticipated ABR. According to the model, the 80 mg, fixed, once-monthly dose is anticipated to result in near

---

maximal achievable reduction in ABR, in which the majority of patients may achieve >75% AT lowering, the therapeutic target. Weight was not a significant covariate in the model, suggesting no advantage to weight-based dosing.

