All patients will be treated for a total of 9 months; patients randomized to the fitusiran treatment arm will receive a total of 9 SC injections of fitusiran. Because the full PD effect of fitusiran is not achieved until approximately 28 days after receiving the first dose, efficacy will be assessed during the final 8 months on study (Day 29 to Month 9). Therefore, the overall fitusiran treatment period is defined as the onset period (Day 1 to Day 28 after receipt of the first dose, during which the AT lowering capacity of fitusiran is increasing but has not yet reached therapeutic levels) plus the efficacy period (Day 29 and after, when the AT lowering capacity of fitusiran has achieved therapeutic target range).

Patients may undergo unplanned or emergency surgery during the study, but must not schedule non-urgent surgery to occur during the study. Perioperative guidance should be followed as specified in Section 6.6.

A Study Steering Committee, composed of experts in the field of hemophilia, will advise the Sponsor on study design and conduct (Section 4.6).

An independent data monitoring committee (DMC) will oversee the safety and overall conduct of this study as described in Section 4.7.

The study design schema is presented in Figure 1. Patients who complete the study may be eligible for an open-label extension study in which patients coming from both the fitusiran and on-demand arms will be administered monthly SC doses of fitusiran.

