#### **6.3.1.2. Bleeding Episode Management Recommendations for Patients in the Fitusiran Treatment Arm**

Given the mechanism of action and pharmacodynamics profile of fitusiran, the BPA dose necessary to safely and effectively treat breakthrough bleeding episodes in patients receiving fitusiran (fitusiran treatment arm) will be lower than standardly prescribed. This is supported by data from the Phase 1 study in which bleed events were managed with factor or BPA, as well as additional modeling and ex vivo spiking data. More detailed information on the clinical experience in bleeding episode management in Phase 1 and Phase 1/2 fitusiran studies, as well as supportive nonclinical studies is provided in the Investigator's Brochure.

After administration of fitusiran, AT lowering will be progressing toward therapeutic levels. As quickly as 7 days after the initial fitusiran dose, the majority of patients will have AT levels at or below 60% residual activity. By 14 days after dosing, it is expected that 94% of patients will have AT lowering of >50%, with a median value of 66.8 %. Based on these AT kinetics, it is

---

recommended that patients continue with their standard BPA regimens for the first 7 days following initiation of fitusiran dosing, with institution of the protocol-specific bleed management guidelines with reduced BPA at Day 8 and beyond (Table 4).

Patients on fitusiran will be provided a written bleed management plan with appropriate dosing of BPA for use during Day 1 through 7, as well as a bleed management plan with dosing for Day 8 and beyond. Thereafter the bleed management plan will be reviewed and updated at monthly visits, and new written plans provided to the patient if dosing changes.

Importantly, during the treatment period, patients should not use BPA or other hemostatic agents as prophylaxis for bleeding episode prevention, including doses related to anticipated hemostatic challenges such as physical activity. For prophylaxis of bleeding episodes in patients who require operative procedures (see Section 6.6).

**Bleed Management Guidelines Day 1 to Day 7:** Patients should be instructed to call the site prior to administering factor or BPA. Patients should continue with their standard BPA regimens.

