3.2.3 Pharmacodynamic Endpoints

- AT activity level over time
- Thrombin generation over time

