6.4.2 Peak Thrombin

Peak thrombin values collected within 48 hours of factor, BPA or antifibrinolytic administration will be excluded from all analysis. Peak thrombin values will be summarized descriptively. In addition, MMRM analyses will be performed on change from baseline in peak thrombin with fixed effects of treatment arm, randomization strata of number of bleeding episodes in the 6 months prior to study entry (≤ 10 vs > 10), visit and baseline peak thrombin level. The covariance structure will be chosen to minimize BIC.

Both analyses in AT and peak thrombin may also be performed on a logarithmic scale. The estimates along with 90% confidence intervals will be back transformed to the original scale.

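### The repeated-measures models for antithrombin lowering and peak thrombin omit treatment-by-visit, so they give one constant arm difference for endpoints defined over time

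*SAP*

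**What the plan says.** SAP 3.2.3 lists "AT activity level over time" as a pharmacodynamic endpoint, with thrombin generation over time beside it. Protocol 3.3 places both among the exploratory endpoints.

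For AT, SAP 6.4.1 plans descriptive summaries and then a model: "mixed model repeated measures (MMRM) analyses will be performed on AT lowering with fixed effects of treatment arm". The remaining fixed effects are the randomization stratum, visit and baseline AT level. On the covariance it says: "A suitable covariance structure will be chosen to minimize Bayesian information criteria (BIC").

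For thrombin, SAP 6.4.2 says "MMRM analyses will be performed on change from baseline in peak thrombin with fixed effects of treatment arm", again with stratum, visit and baseline value, and again with the covariance chosen by BIC. Both analyses may also be run on a log scale, in which case "The estimates along with 90% confidence intervals will be back transformed to the original scale".

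No section adds an interaction. Protocol 8.2.6 promises descriptive summaries by scheduled visit. It allows repeated-measures models where appropriate but names no terms.

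**The concern.** With arm and visit entered only as main effects, the two arms have parallel profiles: the difference at Day 15 must equal the difference at Day 253. The protocol does not expect that. Protocol 4.1 describes Days 1 to 28 as the period "during which the AT lowering capacity of fitusiran is increasing but has not yet reached therapeutic levels", and Table 1 schedules AT and thrombin generation at Day 15.

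Two things follow. First, the model planned for a time-course endpoint cannot estimate an arm difference by visit. Second, when the true difference varies, the one coefficient is a weighted average over visits. Its weights come from a covariance structure selected from the data, so the quantity being estimated is not fixed in advance. The SAP does not say what the single estimate is meant to represent.

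At stake is the model-based description of AT lowering and thrombin generation. The annualized bleeding rate analyses do not use these models.

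**Working it through.** The plan states no figure to reproduce, so the check is algebra followed by an illustration.

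**Model as listed.** For arm *a* and visit *j*:

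E[Y] = b0 + b1·arm + b2·stratum + v_j + b3·baseline

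The arm difference is b1 at every *j*. On the log scale it becomes one constant ratio.

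**What b1 estimates.** With complete data, the fitted b1 averages the visit-specific differences with weights V⁻¹1 / (1′V⁻¹1), where V is the within-patient covariance. Call the Day 15 weight *w*. If the difference is 66.8 at Day 15 and a constant plateau P afterwards:

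b1 = P − w·(P − 66.8)

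**Inputs.**
- Visits: the 11 post-baseline visits in Protocol Table 1 from Day 15 to Day 253 (15, 29, 43, 57, 85, 113, 141, 169, 197, 225, 253). That all 11 enter the model is an assumption; SAP 6.4 does not say.
- Day 15, fitusiran: 66.8, from Protocol 6.3.1.2, which expects by 14 days "AT lowering of >50%, with a median value of 66.8" per cent. This median is used as a mean.
- Plateau: 80 to 90, from Protocol 1.4, "approximately 10% to 20% residual AT activity at a dose of 1.8 mg/kg and at fixed doses of 50 mg and 80 mg".
- On-demand arm: 0 (assumed).

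**Day 15 weight.**
- Independence or compound symmetry: 1/11 = 0.091.
- AR(1) in visit order: 1/(11 − 9ρ). With ρ = 0.5, 1/6.5 = 0.154; with ρ = 0.8, 1/3.8 = 0.263.

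**Results (percentage points).**

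| Plateau | Structure | b1 | Error at Day 15 | Error later |
|---|---|---|---|---|
| 80 | Compound symmetry | 80 − 0.091 × 13.2 = 78.8 | +12.0 | −1.2 |
| 80 | AR(1), ρ = 0.5 | 78.0 | +11.2 | −2.0 |
| 80 | AR(1), ρ = 0.8 | 76.5 | +9.7 | −3.5 |
| 90 | Compound symmetry | 90 − 0.091 × 23.2 = 87.9 | +21.1 | −2.1 |
| 90 | AR(1), ρ = 0.5 | 86.4 | +19.6 | −3.6 |
| 90 | AR(1), ρ = 0.8 | 83.9 | +17.1 | −6.1 |

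**With the 80 mg figure.** Protocol 1.2.2.3 gives a mean maximal reduction of 85.9% at 80 mg. Using it as the plateau under compound symmetry, b1 = 85.9 − 19.1/11 = 84.2, which is 17.4 too high at Day 15 and 1.7 too low later. Because the visit effect is shared and allocation is 2:1, the fitted on-demand value at Day 15 is (2/3)(66.8 − 84.16) = −11.6, against a true 0.

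**Effect of the covariance choice alone.** At a plateau of 85, b1 is 83.3 under compound symmetry and 80.2 under AR(1) with ρ = 0.8. A purely hypothetical case shows that the average need not lie inside the range of true differences. Heterogeneous compound symmetry with ρ = 0.5 and a Day 15 SD 1.25 times that of later visits gives w = −0.08/0.92 = −0.087 and b1 = 86.6, above the true difference at every visit.

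**With treatment-by-visit added.** The same inputs return 66.8 at Day 15 and the plateau at later visits under every structure.

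The documents give no visit-level thrombin values, so the peak thrombin model can be faulted on structure only.

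**The case against.** The strongest reply is that little depends on these models. The endpoints are exploratory and outside the hierarchy in SAP 5.7, and the protocol makes repeated-measures modelling optional. The by-visit descriptive summaries will show the course in each arm. On-demand patients receive no AT-lowering drug, so the fitusiran profile alone conveys most of what a by-visit AT contrast would. All of this stands, and it limits the importance of the point. However, the SAP does commit to the models, and descriptive summaries do not supply an adjusted arm difference with an interval at each visit.

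The magnitudes can also be challenged. The 90% end of the plateau pools several doses, whereas the 80 mg means in Protocol 1.2.2.3 are 85.9% to 87%. Those are maximum reductions, and predose visit means may be lower. At 87% the compound-symmetry error at Day 15 is 18.4. At 75%, the therapeutic target, the Day 15 error falls to 7.5, 6.9 or 6.0 under the three structures, and the later error to 0.7, 1.3 or 2.2. The 10 to 21 range therefore belongs to the stated inputs and is not a bound. The heterogeneous example rests on values with no support in the documents.

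Finally, many statisticians take an MMRM to include the interaction by convention. Here the terms are spelled out without it, so a programmer following the SAP would fit parallel profiles.

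**Conclusion.** The concern holds. As written, both models give one arm difference for all visits, while the protocol's own account of AT lowering implies that the difference changes between Day 15 and the plateau. That structural conclusion needs none of the illustrative values.

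For AT, the size is roughly 10 to 21 points too large at Day 15 and 1 to 6 too small later. This assumes a Day 15 value of 66.8%, a plateau of 80% to 90%, no lowering on demand, 11 complete visits, and compound symmetry or AR(1) with ρ of 0.5 or 0.8. A lower plateau shrinks these errors. For peak thrombin the size is unknown.

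The consequence is modest. No confirmatory test or bleeding-rate result is affected, and the onset-period split at Day 28 comes from earlier modelling (Protocol 1.3). It is still worth correcting because the change is small and the better model is clear.

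**What to change.** In SAP 6.4.1 and 6.4.2, add a treatment-by-visit interaction to the fixed effects. Report least-squares means and arm differences with confidence intervals at each visit. If one overall number is wanted, define it explicitly, for example as the equally weighted average over the efficacy-period visits. Baseline-by-visit is optional.

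The same edit should name the visits that enter the models. AT follow-up visits exist only for some fitusiran patients, and Day 2 and Day 8 samples only for East Asian patients at East Asian sites.

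With two arms and 11 post-baseline visits, the interaction costs (2 − 1) × (11 − 1) = 10 degrees of freedom per model. Baseline-by-visit would take another 10. No new data are needed and the testing hierarchy is unchanged.

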6.4.2 Peak Thrombin

Peak thrombin values collected within 48 hours of factor, BPA or antifibrinolytic administration will be excluded from all analysis. Peak thrombin values will be summarized descriptively. In addition, MMRM analyses will be performed on change from baseline in peak thrombin with fixed effects of treatment arm, randomization strata of number of bleeding episodes in the 6 months prior to study entry (≤ 10 vs > 10), visit and baseline peak thrombin level. The covariance structure will be chosen to minimize BIC.

Both analyses in AT and peak thrombin may also be performed on a logarithmic scale. The estimates along with 90% confidence intervals will be back transformed to the original scale.

6.4.3 AT Lowering and Peak Thrombin

Correlation between AT (actual AT levels and AT lowering) and thrombin will be computed on paired assessments, where both parameters are measured on the same day. Log transformation may be used.

6.5 Pharmacokinetic Analysis

Non-compartmental analysis for PK parameter estimation in East Asian patients from East Asian sites is described in this analysis plan. Population PK analysis is planned for all patients in the study and will be described in a separate population PK analysis plan.

Pharmacokinetic parameters to be estimated using noncompartmental analysis will include, but will not be limited to: maximum plasma concentration (C_{max}), time to maximum plasma concentration (t_{max}), elimination half-life ($t_{1/2\beta}$), area under the concentration-time curve (AUC), apparent clearance (CL/F), and apparent volume of distribution (V/F). Other parameters may be calculated, if deemed necessary. PK analysis is not in the scope of this SAP and will be reported separately.

6.6 Safety Analyses

Safety analyses will be conducted using the Safety Analysis Set. All safety summaries will be presented by treatment arm and may include the overall column as specified.

6.6.1 Study Duration, Study Drug Exposure and Compliance

Study duration in treatment period in days is calculated as EOS/ET visit date – Day 1 visit date (or date of first dose of study drug for fitusiran arm) +1. Total study duration including AT follow-up in days is calculated as date of last follow-up – Day 1 visit date (or date of first dose of study drug for fitusiran arm) +1. The number of patients in each 2 months interval and summary statistics for the study duration by treatment group will be presented.

Exposure to study medication in days and the total number of study drug SC administrations received will be summarized for fitusiran arm.

Duration of treatment exposure in days is calculated as date of the last dose of study drug – the date of the first dose of study drug + 28. The number 28 is the number of days between two scheduled doses of study drug. For example, if the last dose of study drug is taken on Day 31, the treatment exposure would be calculated as $(31-1) + 28 = 58$ days.

Dose interruptions and compliance are not taken into account for duration of exposure.

Fitusiran treatment compliance will be calculated as the total mg dose received as the percentage of total mg dose expected to receive. Fitusiran treatment compliance will be summarized.

6.6.2 Adverse Events

All AEs will be coded using the MedDRA coding system (version used at the time of the database lock) and displayed in tables and data listings using system organ class (SOC) and preferred term (PT).

Analyses of AEs will be performed for those events that are considered treatment-emergent, and will be referred to as TEAEs. Treatment emergent AE is defined as any AE with onset date after first dose of fitusiran for fitusiran arm or after Day 1 visit for the on-demand arm. Events with a fully or partially missing onset date will be assumed to be treatment emergent unless it can be unequivocally determined (from the partial onset date and/or a partial or complete stop date) that the event occurred prior to the first dose for fitusiran arm or prior to Day 1 visit for the on demand arm.

AEs will be summarized by the numbers and percentages of patients reporting at least one AE, having at least one AE by primary System Organ Class (SOC) and Preferred Term (PT). A patient with multiple occurrences of an AE will be counted only once in the respective AE category. Patients who report multiple occurrences of the same AE (preferred term) will be classified according to the most related or most severe occurrence, respectively.

All AE summaries will be presented (frequency counts and percentages) by system organ class and/or preferred term, unless specified otherwise. The SOC will be presented alphabetically and the preferred term will be sorted within each SOC in decreasing order of frequency in the fitusiran arm.

The following events are considered to be AEs of special interest (AESI):

- ALT or AST elevations $>3 \times$ ULN
- Suspected or confirmed thromboembolic events
- Severe or serious injection site reactions (ISRs), ISRs that are associated with a recall phenomenon (reaction at the site of a prior injection with subsequent injections) or, those that lead to temporary dose interruption or permanent discontinuation of study drug.
- Systemic injection associated reactions (IARs), defined as hypersensitivity reactions which are related or possibly related to study drug.

An overall summary of AEs will include the number and percentage of patients with any AE, any AE assessed by the Investigator as related to study drug (fitusiran only, possibly related or definitely related), any severe AE, any severe AE related to study drug, any serious AE (SAE), any SAE related to study drug, any AE/SAE of special interest; any AE/SAE leading to study drug discontinuation, any study drug related AE/SAE leading to study drug discontinuation, any AE/SAE leading to study withdrawal any study drug related AE/SAE leading to study withdrawal, AE potentially consistent with COVID-19 and any deaths. The overall summary of AEs will also be provided by hemophilia type.

Tabulations by SOC and PT will be produced for the following:

- all AEs;
- AEs by severity;
- AEs by hemophilia type
- all SAEs;
- AEs related to study drug (fitusiran arm only);
- AEs related to study drug by hemophilia type (fitusiran arm only);
- SAEs related to study drug (fitusiran arm only);
- SAEs related to study drug by hemophilia type (fitusiran arm only);
- AESI;
- AESI by hemophilia type;
- SAEs of special interest;
- SAEs of special interest by hemophilia type;
- AEs leading to study drug discontinuation (fitusiran arm only);
- SAEs leading to study drug discontinuation (fitusiran arm only);
- AESIs leading to study drug discontinuation (fitusiran arm only);
- Serious AESIs leading to study drug discontinuation (fitusiran arm only);
- AEs leading to study withdrawal;
- SAEs leading to study withdrawal.
- AEs potentially consistent with COVID-19

COVID-19 infection will be identified based on the search term list in Appendix 8.2.

Tabulations by PT in decreasing order in frequency in the fitusiran arm will be produced for the following:

- all AEs;
- all AEs by hemophilia type;
- all SAEs;
- AEs related to study drug (fitusiran arm only);
- SAEs related to study drug (fitusiran arm only);

All AEs collected will be listed along with the information collected on those AEs, eg, AE relationship to study drug, AE outcome etc. AEs that are not treatment-emergent will be flagged in the listings. By-patient listings will also be provided for the following: all patient deaths, all SAEs, and all AEs leading to study drug discontinuation or study withdrawal, all AEs leading to death, AEs potentially consistent with COVID-19.

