**Note:**

- See Section 7 for study assessment instructions.
- Any Screening assessments performed within 7 days prior to baseline do not need to be repeated at the Baseline visit.
- Rescreening of patients is permitted with consultation of the study Medical Monitor.
- Laboratory parameters are described in Section 7.5.5 and listed in Table 5.
- As clinical research parameters, TG, D-dimer, and all other non-safety laboratory parameter results will not be communicated to sites. AT and factor results will be provided at screening for confirmation of eligibility. AT results will be provided at AT follow-up visits for monitoring.
- When scheduled at the same time points, vital signs and 12-lead ECGs will be performed before the physical examinations and blood/urine sample collections.
- Unless otherwise specified, assessments on dosing days are predose.

- a Not required at Early Termination Visit for patients who complete assessment at EOT Visit and subsequently Early Terminate.
- b Patients in the fitusiran treatment arm who discontinue IMP dosing for any reason and agree to complete the remaining assessments through the EOS/ET visit and AT follow-up and may receive treatment consistent with local standard practice for their disease per Investigator judgment, once AT levels return to ~60% (per the central laboratory) or per Investigator discretion in consultation with the study Medical Monitor. For patients who withdraw from the study early and do not consent to complete remaining assessments through the EOS/ET visit and AT follow-up visits, every effort should be made to conduct the assessments performed at the EOS/ET visit.
- c Patients in the fitusiran treatment arm not enrolling in the extension study will complete AT F/U visits at monthly intervals following final fitusiran dose until AT activity level returns to ~60% (per the central laboratory) or per Investigator discretion in consultation with the study Medical Monitor.
- d The complete medical history/disease history (ie, including bleeding episode and treatment history over the prior 6 months) to be recorded at Screening.
- e Randomization may occur within 3 days prior to Day 1.
- f eDiary training will be completed at the Clinic at Screening (see Section 7.2.1).
- g A full physical exam will be performed at Screening only; a directed physical exam will be performed at all other visits (see Section 7.5.3).

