- q All patients will be tested for antibodies to fitusiran at the Screening visit. After randomization, testing for antibodies to fitusiran will be performed in the fitusiran treatment arm only.
- r Blood samples for PK analysis will be collected at the time points listed in Table 7 in all fitusiran arm patients. In East Asian patients in the fitusiran arm at East Asian sites, blood samples for PK analysis will be collected at the time points listed in Table 8 (which includes all those time points listed in Table 7), and pooled urine samples will be collected for PK analysis at the time points listed in Table 9.
- s Must be completed at the clinic. Will be collected at EOS visit; not collected at ET visit.
- t Will include review of entries, (symptoms of bleed events, bleed causality, bleed severity, doses administered), whether appropriate site contact occurred regarding treatment of bleeds, and review of patient bleed management plan and recommendations and requirements for site contact regarding dosing.
- u It is strongly preferred that BPA administration and bleeding events are entered in the eDiary immediately or within 24 hours. Additional patient follow-up may be required as described in Section 7.2.1. Patients in the fitusiran treatment arm who present in the clinic with symptoms characteristic of a potential bleeding episode should have assessments completed per Table 2.
- v Perioperative assessment safety and hemostatic efficacy only in patients undergoing operative procedures while on study (see Table 10).
- w AEs will be monitored and recorded from date of signed informed consent through Follow-Up. Signs and symptoms of thrombosis will be evaluated at every visit (see Section 6.5)
- x In addition to recording concomitant medications, documented history of prior medications will be collected during Screening.

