#### Recording Adverse Events

The Investigator is responsible for recording non-serious AEs and SAEs that are observed or reported by the patient after the time when the informed consent is signed regardless of their relationship to IMP through the end of study. Non-serious AEs will be followed until the end of study. SAEs will be followed until satisfactory resolution, until baseline level is reached, or until the SAE is considered by the Investigator to be chronic or the patient is stable, as appropriate.

All AEs must be recorded in the source records for the clinical study center and in the eCRF for the patient, whether or not they are considered to be drug-related. Each AE must be described in detail: onset time and date, description of event, severity, relationship to investigational drug, action taken, and outcome (including time and date of resolution, if applicable).

For SAEs, record the event(s) on both the eCRF and the SAE form.

For AEs that are considered AESI (Section 7.5.6.1), the Sponsor or its designee should be notified within 24 hours using a supplemental AESI eCRF. Additional clinical and laboratory information may be collected; see Section 6.2.3.1 regarding monitoring for liver abnormalities.

Refer to the eCRF completion guidelines for details on reporting events in the supplemental AESI eCRF.

Since bleeding episodes are recorded as an efficacy assessment of fitusiran, these will not be treated as AEs unless they meet any of the SAE criteria listed in Section 7.5.6.1. The manifestation and frequency of bleeding episodes is an efficacy indicator of this study and ABR is the focus of the primary and secondary efficacy analyses.

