#### **8.2.8. Safety Analyses**

Extent of exposure will be summarized. Safety will be based on all AEs having onset (start or worsening in severity) within the study and on the Safety Analysis Set. Incidence of AEs, AEs by maximum severity, AEs by relationship to study medication, SAEs and AEs leading to discontinuation of treatment will be presented.

---

Descriptive statistics will be provided for clinical laboratory data, ECG and vital signs. Laboratory shift tables from baseline to worst post-baseline values may be presented.

Other safety summaries will be presented as appropriate. Further details will be specified in the SAP.

Adverse events will be classified according to the MedDRA System Organ Class and Preferred Term. Prior and concomitant medications will be classified according to the World Health Organization (WHO) drug dictionary.

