**9.1.4. End of the Study**

The end of the study is defined as last patient last visit.

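### Treatment-emergent AEs have no end date, so AT follow-up, which only some fitusiran patients have, can raise that arm's crude AE percentages through extra observation time alone

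*SAP*

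**What the plan says.** SAP 6.6.2 (Adverse Events) limits the AE analyses to treatment-emergent events, defined as "any AE with onset date after first dose of fitusiran for fitusiran arm or after Day 1 visit for the on-demand arm". The definition has a start for each arm and an end for neither. The same section gives the summary measure: "AEs will be summarized by the numbers and percentages of patients reporting at least one AE". SAP 6.6 presents safety summaries by arm, and 6.6.2 plans no exposure-adjusted rate.

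The protocol does not close the window. Section 8.2.8 states: "Safety will be based on all AEs having onset (start or worsening in severity) within the study". On collection, Table 1 footnote w says "AEs will be monitored and recorded from date of signed informed consent through Follow-Up". Section 7.5.6.2 (Recording Adverse Events) words it differently: events are recorded "regardless of their relationship to IMP through the end of study". Section 9.1.4 adds: "The end of the study is defined as last patient last visit".

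The follow-up phase belongs to one arm. Table 1 footnote c says: "Patients in the fitusiran treatment arm not enrolling in the extension study will complete AT F/U visits at monthly intervals following final fitusiran dose". It ends when AT activity is back to about 60%, or at the investigator's discretion in consultation with the Medical Monitor. Protocol 4.2 puts maximum time on study, screening included, at 17 months for these patients. The maximum is 11 months for everyone who enters the extension and for on-demand patients who do not.

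**The concern.** If the plan is followed as written, the two columns of an AE table can cover different lengths of time. A fitusiran patient who declines the extension goes on contributing events after EOS, and no on-demand patient does. A percentage of patients with at least one event can only rise with more observation time, so the fitusiran column can be higher even if the drug causes nothing.

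The tables exposed are those comparing the arms: all AEs, AEs by severity, SAEs, AEs of special interest (AESIs), AEs leading to study withdrawal, and COVID-19 events. AESIs matter most. They include suspected or confirmed thromboembolic events and transaminase elevations, and footnote w has signs of thrombosis evaluated at every visit, so these events are actively looked for. A reader of the tables could not separate an arm difference from a difference in follow-up.

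**Working it through.** **1. The plan's own durations.** Table 1 allows up to 60 days of screening, about 2 months. Then 2 + 9 = 11 months, and 11 + 6 = 17 months. Both figures in protocol 4.2 reproduce. Counted from Day 1, the maximum window is 15 months for a fitusiran patient in AT follow-up and 9 months for anyone else, a ratio of 15/9 = 1.67.

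**2. In days.** EOS is Day 253 (Table 1). Taking 6 months as 180 days after EOS, the longest window ends at Day 253 + 180 = 433.

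**3. Effect on a crude percentage.** Assume a constant hazard, equal in both arms. Let r be the risk by Day 253 and f the share of fitusiran patients who do not roll over, each followed to Day 433.

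- Risk by Day 433: r* = 1 − (1 − r)^(433/253)
- Fitusiran-arm percentage: (1 − f)·r + f·r*

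For r = 30%: r* = 1 − 0.70^1.711 = 45.7%. With f = 20%: 0.8 × 30 + 0.2 × 45.7 = 33.1%. With f = 50%: 0.5 × 30 + 0.5 × 45.7 = 37.8%.

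| On-demand arm | Risk by Day 433 | Fitusiran arm, f = 20% | Fitusiran arm, f = 50% |
|---|---|---|---|
| 30% | 45.7% | 33.1% | 37.8% |
| 50% | 69.5% | 53.9% | 59.7% |

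The same formula in months (exponent 15/9) gives 33.0% and 37.4% for the 30% event. For a 5% event it gives 5.6% and 6.6%. At f = 0 the difference is zero.

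**4. In patients.** With 36 planned fitusiran patients (protocol 1.3), a 30% event is expected in 10.8. The excess is 36 × 3.1% = 1.1 patients at f = 20%, and 36 × 7.8% = 2.8 at f = 50%.

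**5. If the 6 months run from the last dose.** Footnote c counts AT follow-up from the final dose. From the last scheduled dose, Day 225, 180 days end at Day 405. Then r* = 1 − 0.70^(405/253) = 43.5%, and the fitusiran percentages are 32.7% and 36.8%. The Day 433 figures are therefore a ceiling.

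**6. How the SAP treats this period elsewhere.** Section 6.6.1 calculates study duration both to EOS/ET and including AT follow-up. Section 5.10 has a separate analysis window after EOS/ET. Section 6.6.7 limits the concomitant-medication tables to the treatment period. Only the AE section makes no distinction.

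**The case against.** **Collection may stop at EOS.** Section 7.5.6.2 can be read that way: SAP 4 and 6.3.1.3 both equate end of study with Month 9, and Table 1 separates EOS from AT follow-up. On that reading the windows match. The definition in 9.1.4 concerns closure of the trial and does not clearly settle one patient's AE window. This stands as an ambiguity. Footnote w still points the other way, and the SAP does not choose between them.

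**The figures are ceilings.** Six months is a maximum, the roll-over share is not stated, and a constant hazard is doubtful because no injections are given in AT follow-up, so new injection reactions should not keep accruing. SAP 5.4 also has the primary safety analysis run once all patients finish 9 months or withdraw, when some AT follow-up may be incomplete. All of this stands. With no AE cut-off stated, however, the window would then depend on enrolment date and data cut.

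**Cutting at EOS/ET could hide events.** AT may still be lowered after the last dose, and removing later AESIs from view would be anti-conservative. This stands, and it shapes the fix.

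**Little is at stake.** Safety is descriptive, all AEs are listed, durations are summarised by group, and the bias runs against fitusiran. This limits the severity, but listings and duration summaries do not correct a percentage.

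**A stronger reading to avoid.** A reader might infer that patients who stopped fitusiran early have the longest window, which would tie the bias to intolerance. The documents do not support this. AT follow-up runs from the final dose, so with 180 days a patient last dosed on Day 57 finishes by Day 237, before EOS, and one last dosed on Day 85 finishes by Day 265. Patients who withdraw and decline follow-up have shorter windows. The long window belongs mainly to those who completed dosing and declined the extension.

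**Conclusion.** The point holds as a gap in the definition that should be closed. With no end date, the crude between-arm AE percentages can compare unequal observation time, and the extra AT follow-up can only push the fitusiran figure up. For a 30% event the upper bound is 33.1% if 20% do not roll over and 37.8% if 50% do not. This rests on equal constant hazards, the full 6 months for each such patient, AE collection through AT follow-up, and assumed roll-over shares. The effect is smaller if follow-up ends earlier, and zero if all roll over or if collection stops at EOS. No type I error is affected, because safety is not tested.

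**What to change.** - **Common window.** In SAP 6.6.2, base the between-arm AE, SAE and AESI tables on onset from first dose (fitusiran) or Day 1 visit (on-demand) to the EOS/ET visit in both arms.
- **Exposure-adjusted rates.** Add them to those tables, because ET dates vary and a common cut-off alone does not equalise follow-up.
- **Nothing hidden.** Keep an all-TEAE table for the fitusiran arm that includes AT follow-up. Tabulate events with onset in AT follow-up, AESIs above all, beside the main table.
- **Reconcile the protocol.** State once whether AE recording stops at EOS or continues through AT follow-up, so that Table 1 footnote w and Section 7.5.6.2 agree.

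The cost is a few lines of SAP wording, one protocol clarification and one or two extra tables. The downside is small: late fitusiran events appear in an adjacent table and not in the between-arm one.
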